#### **4.4.2 Survival follow-up patient**

If another treatment is initiated due to progressive disease or other reasons, the patient will be followed for survival until death or End of Study (see section 7.5.3 *Survival Follow-Up*). The final clinical follow-up visit ( [REDACTED] ) should then be scheduled to collect endpoint data ( [REDACTED] ) as close to the start of new treatment as possible.

#### **4.4.3 Off-study patient**

The patient will be withdrawn from participation in this trial at any time if any of the following criteria are met:

1. The patient requests to be removed from the trial and withdraws consent.
2. Lost to follow-up/serious noncompliance to protocol.
3. The trial is terminated.

No further data, except for survival, will be collected for these patients (see section 7.5.3 *Survival Follow-Up*).

### **4.5 Replacement of Patients**

If a patient does not complete [REDACTED] of LOAd703 and atezolizumab (for a reason other than LOAd703- or atezolizumab-attributed toxicity), this patient will be replaced by another subject in order to meet the minimum criteria for safety (see section 10.2 *Sample Size*).

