Prior to each LOAD703 and/or atezolizumab treatment (within -2 days), the Investigator must meet the patient to perform a complete AE evaluation (including laboratory values) and assess the toxicity screening to assure that the patient is able to receive next treatment (see sections 7.2.5 *Continuation Criteria* and 4.4 *Withdrawal of Patients*).

[REDACTED] Radiological assessment will be performed at enrollment and thereafter every two months.

[REDACTED], the patients will undergo the final follow-up visit and thereafter enter the survival follow-up. The informed consent form includes a specific question about whether the patient consents to the study team following up their condition every 4 months after the final follow-up visit at the clinic.

OS will be recorded for the patients until death or until End of Study. The survival data may be collected via medical records (SWE, US) or by telephone/email from the Investigator or research nurse/coordinator (US) (see 7.5.3 *Survival Follow-Up*). OS will be reported as a descriptive addendum to the study report.

When the first patient in a cohort has received [REDACTED]

[REDACTED] the next two patients in the cohort can begin treatment but must start treatment at least one day apart (24 hours). Note that enrollment and screening is allowed if slots are available in a cohort at any time. Slots are distributed upon request by the CRO (see section 4.3 for more information).

[figure not shown]
If a patient does not complete [REDACTED] (for a reason other than LOAD703 attributed DLT), this patient will be replaced by another subject and not regarded as a DLT evaluable. The BON design to evaluate safety allows for continuous DLT assessments and cohort sizes larger than 3 and will thus continue throughout the study.

The decision to escalate dose is taken by the Sponsor after a safety meeting including the Sponsor, CRO, Clinical Project Manager (for taking notes only), Medical Advisor and at least 2 of the site Principal Investigators as a minimum. The maximum tolerated dose (MTD) level will be expanded for continued safety and efficacy evaluation and at least 25 efficacy evaluable patients will be

enrolled at MTD. By using the BOPIN design, the actual MTD is therefore determined at the end of the study (see section 5.6.9 LOAd703 Maximum Tolerated Dose (MTD)). The justification of cohort sizes and the sample size calculation are described in section 10.0 STATISTICS.

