## 5.5 Dose Limiting Toxicity (DLT)

As LOAd703 will be dose escalated, the patients will be monitored for dose limiting toxicity (DLT). DLT is defined as any grade 3 or higher toxicity (CTCAE Version 5.0) that is attributed (definitely, possibly or probably) to LOAd703. A DLT attributed to LOAd703 will lead to dose reduction (see 5.6.8 *LOAd703 Dose Modifications*).

Phase I: The first patient on each dose level must have been evaluated for DLT [REDACTED] before patient 2 and 3 in the same cohort can start treatment. Patient 2 and 3 should start treatment at least 24 hours apart.

All 3 patients in the cohort must have been evaluated for DLT before decision on dose escalation is taken for the next cohort.

Phase II: Patient enrollment continues and evaluation for DLTs [REDACTED] (see 10.2 *Sample Size*).

Toxicity attributed to atezolizumab will not be assessed as DLTs in the study but can still lead to dose modifications (see 5.7.7 *Atezolizumab Dose Modifications*).

If a patient experiences an AE grade 3 or higher that can be attributed to the LOAd703 injection procedure (i.e., a bacterial infection, injection site pain, etc.), to disease, or another unrelated cause, it is not a DLT. SAEs due to injection procedure can lead to change of injection procedure (such as change of lesion) instead of treatment discontinuation, depending on the type of AE and the risk of recurrence of the AE.

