### **9.2.2 Attribution Definitions**

The Investigator will attempt to assess the relationship of the event to the study drugs separately. An AE is considered to be associated with the use of any or both of the investigational products if the attribution is determined as possible, probable or definite. Attribution of AEs will be recorded in the CRF as:

- **Unrelated**: The AE is clearly NOT related to LOAd703 (or atezolizumab).
- **Unlikely**: The AE is doubtfully related to LOAd703 (or atezolizumab).
- **Possible**: The AE may be related to LOAd703 (or atezolizumab).
- **Probable**: The AE is likely related to LOAd703 (or atezolizumab).
- **Definite**: The AE is clearly related to LOAd703 (or atezolizumab).

Attribution will be specified for LOAd703, atezolizumab, treatment procedure (i.e., intratumoral injection and/or intravenous infusion), disease or other.

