## 10.2 Sample Size

### 10.2.1 Safety

The study will be conducted using a Bayesian Optimal Interval (BOIN) design with a target DLT rate of 0.3. This design has algorithmic escalation/de-escalation rules like a traditional 3+3 design but allows for specification of the target DLT rate and expanded accrual beyond N=6 with continued consistent toxicity monitoring (i.e., the assessment of DLT rate continues throughout the study which gives a well-defined safety evaluation of Phase I/II studies).

Two LOAd703 dose levels will be tested together with a fixed dose of atezolizumab. The BOIN design allows for enrollment of 3 patients in a cohort and the number of patients with DLT determines whether additional patients are treated with the current dose or if the dose is decreased or increased. In general, we will escalate the dose if the observed toxicity rate at the current dose is  $\leq 0.2365$ , and we will de-escalate the dose if the observed toxicity rate at the current dose is  $\geq 0.3585$ . If the observed toxicity rate is between 0.2365 and 0.3585, 3 additional patients will be treated at the current dose. For cohorts of size 3, the decision boundaries are shown in Table 3.

Additional cohorts will be added in the unlikely event that more than N=25 participants at a single dose level are needed.

[figure not shown]
Table 2. DLT Regulation of Dose Escalation

Number of Patients treated in a Defined Dose Cohort	3	6	9	12	15	18	21	24	25
Escalate dose if number of DLT $\leq$	0	1	2	2	3	4	4	5	5
Treat additional 3 patients at current dose if number of DLT=	1	2	3	3,4	4,5	5,6	5-7	6-8	6-8
De-escalate dose if number of DLT $\geq$ *	2	3	4	5	6	7	8	9	9
Eliminate** dose level and all higher doses from further use if number of DLT $\geq$	3	4	5	7	8	9	10	11	12

\* At the lowest dose level, if the recommendation is to de-escalate AND the dose level has not been eliminated from consideration, 3 additional patients can be accrued at the same dose level; otherwise the trial will be stopped.

\*\* Note that if the DLT level reach the elimination limit, this dose level is abandoned from the study independently of DLT events at lower dose levels.

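### Protocol 4.5 and 5.1 give opposite replacement instructions for patients who stop early for drug toxicity that is not a LOAd703 DLT, and 5.5 leaves events attributed to both drugs ambiguous

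*Protocol*

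**What the plan says.** **Replacement.** Protocol 4.5 covers a patient who does not complete a stated (redacted) amount of both drugs: "for a reason other than LOAd703- or atezolizumab-attributed toxicity), this patient will be replaced by another subject". It gives the purpose as meeting the minimum safety criteria and points to section 10.2. Protocol 5.1 covers the same situation with a different exception: "for a reason other than LOAD703 attributed DLT), this patient will be replaced by another subject and not regarded as a DLT evaluable".

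**What counts as a DLT.** Protocol 5.5: "DLT is defined as any grade 3 or higher toxicity (CTCAE Version 5.0) that is attributed (definitely, possibly or probably) to LOAd703". Later in the same section: "Toxicity attributed to atezolizumab will not be assessed as DLTs in the study". SAP 6.4.1.1 repeats both statements. Protocol 9.2.2 says "The Investigator will attempt to assess the relationship of the event to the study drugs separately" and allows one event to be associated with both products.

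**Use of the rate.** Protocol 10.2.1 and SAP 7.8.1 set a "BOIN) design with a target DLT rate of 0.3", with escalation at or below 0.2365 and de-escalation at or above 0.3585. SAP 7.7.2 divides by DLT-evaluable subjects and names as MTD the dose whose isotonic estimate lies closest to 0.3. Its definition of DLT-evaluable is redacted.

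**The concern.** The two exception clauses are both readable, and they differ. A patient who falls short of both completion thresholds because of an atezolizumab toxicity, or because of (say) a grade 2 LOAd703 toxicity, is not replaced under 4.5 but is replaced and removed from the DLT count under 5.1. Sites and the safety meeting can therefore reach different denominators from the same facts.

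The numerator has a smaller problem. Because each drug is attributed separately, a grade 3 event can be rated possible for both. The definition in 5.5 makes it a DLT; the atezolizumab sentence, which does not say *only*, can be read to exclude it.

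The plan leans on the written rule. SAP 7.6.5.3 plans no data monitoring committee and leaves the escalation decision to the sponsor after a safety meeting. If the rule has two versions, a disputed case has to be settled by judgement once the outcome is known.

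**Working it through.** **1. Reproduce the plan's boundaries.** Take φ = 0.3, with φ1 = 0.6φ = 0.18 and φ2 = 1.4φ = 0.42. These multipliers are usual BOIN defaults that the documents do not state.

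- λe = ln(0.82/0.70) / ln[(0.30×0.82)/(0.18×0.70)] = 0.2365
- λd = ln(0.70/0.58) / ln[(0.42×0.70)/(0.30×0.58)] = 0.3585

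floor(nλe) and ceil(nλd) give the printed escalate and de-escalate rows. The elimination row follows from Pr(p > 0.3 | data) > 0.95 with a Beta(1,1) prior (prior and cut-off again assumed). All 27 entries match, so the table itself is sound. The question is what goes into it.

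**2. Set the replacement rules side by side.**

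| Reason for stopping early | Protocol 4.5 | Protocol 5.1 |
|---|---|---|
| LOAd703-attributed DLT | not replaced | not replaced |
| Atezolizumab-only toxicity | not replaced | replaced, not evaluable |
| LOAd703 toxicity that is not a DLT | not replaced | replaced, not evaluable |
| Reason other than drug toxicity | replaced | replaced, not evaluable |

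The rules conflict in the two middle rows. 4.5 never says that an unreplaced patient is DLT-evaluable. That step is inferred from its stated safety purpose and its pointer to 10.2.

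**3. First cohort of three, one disputed patient.** Let p be the true DLT rate, with patients independent. If the patient is kept as a non-DLT, two others decide: P(escalate) = (1−p)² and P(2 or more DLTs) = p². If replaced, three patients decide: P(escalate) = (1−p)³ and P(2 or more DLTs) = 3p²(1−p) + p³.

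| Assumed p | P(escalate), kept | P(escalate), replaced | P(≥2 DLTs), kept | P(≥2 DLTs), replaced |
|---|---|---|---|---|
| 0.1 | 0.81 | 0.729 | 0.01 | 0.028 |
| 0.2 | 0.64 | 0.512 | 0.04 | 0.104 |
| 0.3 | 0.49 | 0.343 | 0.09 | 0.216 |
| 0.4 | 0.36 | 0.216 | 0.16 | 0.352 |

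**4. Larger cohorts.** Hold the DLT count fixed and remove one patient from the denominator.

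- n = 6: 2/6 = 0.333 (stay) becomes 2/5 = 0.400 (de-escalate zone).
- n = 9: 2/9 = 0.222 (escalate) becomes 2/8 = 0.250 (stay).
- n = 12: 4/12 = 0.333 (stay) becomes 4/11 = 0.364 (de-escalate zone).
- n = 15, 18, 21, 24: no decision changes at any DLT count.
- n = 25: only 11 DLTs is affected (de-escalate at 25, eliminate at 24).

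Two disputed patients can still matter at 15: 5/15 = 0.333 (stay) against 5/13 = 0.385 (de-escalate zone). The reduced denominators apply before any replacement is treated, so this step shows sensitivity rather than scheduled decisions. A replacement's own outcome could still add a DLT.

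**5. Event attributed to both drugs.** In the n = 3 column, counting one such event moves 0/3 to 1/3 (escalate to add three), 1/3 to 2/3 (add three to de-escalate) or 2/3 to 3/3 (de-escalate to eliminate). As an illustration, assume a LOAd703-only DLT rate of 0.20 plus a shared rate d, counted as DLTs.

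| d | P(escalate), n = 3 | P(9 or more DLTs), n = 25 |
|---|---|---|
| 0 | 0.80³ = 0.512 | 0.047 |
| 0.05 | 0.75³ = 0.422 | 0.149 |
| 0.10 | 0.70³ = 0.343 | 0.323 |
| 0.15 | 0.65³ = 0.275 | 0.533 |

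The two issues meet when a patient stops early because of a shared event. If it is a DLT, the patient counts as one DLT under 5.1. If it is not, 5.1 removes the patient altogether.

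**The case against.** **On the replacement rules**, the best defence is redaction. The completion thresholds, the definitions of the DLT period and of an evaluable patient, and the SAP definition of DLT-evaluable are all hidden, and a definition based on exposure or observation time could settle evaluability. That stands as a limit on the denominator inference. It does not remove the conflict over replacement, because both exception clauses are visible. A reader might also infer that the SAP must contradict one protocol section whichever definition it holds; that cannot be asserted about unseen text.

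**On shared events**, the defence largely succeeds. The definition in 5.5 already covers any event at least possibly attributed to LOAd703, and the atezolizumab sentence reads naturally as toxicity attributed to that drug alone. A reader might call this a flat contradiction. It is an ambiguity, which remains because the limiting word is missing and 9.2.2 allows dual attribution.

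**Other stronger readings fail:**

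- One might set 1/3 = 0.333 against 1/2 = 0.50 and say that 5.1 triggers de-escalation. Two patients are not a decision point: 5.1 requires replacement, 5.5 requires all three to be evaluated before an escalation decision, and the table starts at three.
- One might say that 5.1 hides tolerability failures. It does not. SAP 7.7 keeps all available data from non-completers, 7.7.3 tabulates events by drug relationship and grade and lists those leading to withdrawal, and 7.3.1 summarises reasons for discontinuation.
- One might expect reconciliation to push the DLT rate in a known direction. Keeping a non-DLT stopper lowers the rate; counting a shared event raises it.

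**Conclusion.** The replacement conflict between Protocol 4.5 and 5.1 is real and should be fixed. With one disputed patient in the first three, P(escalate) differs by 0.147 at an assumed true DLT rate of 0.3 (0.49 against 0.343) and by 0.128 at 0.2 (0.64 against 0.512). These figures assume independent patients and that 4.5 leaves the patient in the denominator as a non-DLT.

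The effect arises only if such a patient occurs, and it is mainly a small-cohort problem: with the DLT count fixed, one such patient changes no decision at 15, 18, 21 or 24. It would therefore go too far to say that every BOIN decision is affected or that the DLT rate has no single value.

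The dual-attribution wording in 5.5 and SAP 6.4.1.1 is a lesser, separate ambiguity, though one event is enough to change the action in a cohort of three. The documents give no visible rate for either kind of case. Confidence is medium, chiefly because the evaluability definitions cannot be seen.

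**What to change.** - Reconcile Protocol 4.5 and 5.1 into one rule covering both replacement and DLT-evaluability, and use it unchanged in SAP 7.7.2.
- State in Protocol 5.5 and SAP 6.4.1.1 one classification for a grade 3 or higher event attributed to both drugs. Which rule and which classification to adopt is for the sponsor and investigators; this point takes no view.
- If any disputed patient or shared event occurred, show the DLT rate and the MTD estimate under both readings, so that a reader can see whether the MTD depends on the wording.

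The cost is short wording edits in three protocol sections and two SAP sections, and possibly one extra row in the DLT table. The reported DLT rate may move in either direction.

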### **4.6 Noncompliance**

All instances of noncompliance and all protocol deviations will be recorded.

## **5.0 TREATMENT OF PATIENTS**

### **5.1 Treatment Overview**

The patients will be informed about the study and sign informed consent whereby they are enrolled in the screening phase of the protocol to determine their eligibility, including assessment of health status and radiological evaluation. Imaging obtained within 3 weeks prior to registration may be used for baseline evaluation at the discretion of the Investigator.

Also, if samples have been taken for routine analysis <7 days prior to screening, the results can be used for eligibility evaluation at the discretion of the Investigator.

Within 7 days after registration, the patients will initiate treatment. The patients will be given up to 12 percutaneous LOAd703 i.t. injections combined with atezolizumab, both administered every 3 weeks. Two cohorts consisting of at least 3 patients per cohort will be evaluated. The LOAd703 dose will be escalated, one dose per cohort, to evaluate the following dose levels:  $1 \times 10^{11}$  VP/injection (cohort 1) and  $5 \times 10^{11}$  VP/injection (cohort 2). The treatment will be administered by percutaneous i.t. injection which may be image-guided depending on the tumor location. Atezolizumab will be administrated IV using a fixed dose (1200 mg/infusion).

On the day of the treatment, [REDACTED]

[REDACTED]. LOAd703 dose, dose modifications and omissions will be

carried out as per instructions in sections 5.6.8 *LOAD703 Dose Modifications* and 7.2.5 *Continuation Criteria*. Atezolizumab dose, dose modifications, and omissions will be instituted per standard guidelines (US: TECENTRIQ® Full Prescribing Information, [REDACTED], Sweden: SmPC/FASS for atezolizumab/TECENTRIQ®) and 7.2.5 *Continuation Criteria*.

Missed LOAD703 or atezolizumab doses will not be made up in order to maintain adherence to the protocol schedule. For details regarding LOAD703 injection and atezolizumab infusion, see sections 5.6.5 *Preparation of LOAD703 Prior to Treatment* 5.6.6 *Administration of LOAD703*, 5.7.4 *Preparation of Atezolizumab Prior to Treatment*, and 5.7.5 *Administration of Atezolizumab*, respectively.

For the first 2 LOAD703 treatments of any trial patient, the patients are monitored overnight. Vital signs will be noted [REDACTED]

Prior to each LOAD703 and/or atezolizumab treatment (within -2 days), the Investigator must meet the patient to perform a complete AE evaluation (including laboratory values) and assess the toxicity screening to assure that the patient is able to receive next treatment (see sections 7.2.5 *Continuation Criteria* and 4.4 *Withdrawal of Patients*).

[REDACTED] Radiological assessment will be performed at enrollment and thereafter every two months.

[REDACTED], the patients will undergo the final follow-up visit and thereafter enter the survival follow-up. The informed consent form includes a specific question about whether the patient consents to the study team following up their condition every 4 months after the final follow-up visit at the clinic.

OS will be recorded for the patients until death or until End of Study. The survival data may be collected via medical records (SWE, US) or by telephone/email from the Investigator or research nurse/coordinator (US) (see 7.5.3 *Survival Follow-Up*). OS will be reported as a descriptive addendum to the study report.

When the first patient in a cohort has received [REDACTED]

[REDACTED] the next two patients in the cohort can begin treatment but must start treatment at least one day apart (24 hours). Note that enrollment and screening is allowed if slots are available in a cohort at any time. Slots are distributed upon request by the CRO (see section 4.3 for more information).

[figure not shown]
If a patient does not complete [REDACTED] (for a reason other than LOAD703 attributed DLT), this patient will be replaced by another subject and not regarded as a DLT evaluable. The BON design to evaluate safety allows for continuous DLT assessments and cohort sizes larger than 3 and will thus continue throughout the study.

The decision to escalate dose is taken by the Sponsor after a safety meeting including the Sponsor, CRO, Clinical Project Manager (for taking notes only), Medical Advisor and at least 2 of the site Principal Investigators as a minimum. The maximum tolerated dose (MTD) level will be expanded for continued safety and efficacy evaluation and at least 25 efficacy evaluable patients will be

enrolled at MTD. By using the BOPIN design, the actual MTD is therefore determined at the end of the study (see section 5.6.9 LOAd703 Maximum Tolerated Dose (MTD)). The justification of cohort sizes and the sample size calculation are described in section 10.0 STATISTICS.

## 5.2 Treatment Schedule for Study Visits

The LOAd703 treatment schedule and study visits over time are described in *Figure 1: Study timeline* and *14.1 Appendix I: Schedule of Events*. LOAd703 treatment is given up to 12 times. Atezolizumab will be administered continuously during study participation if judged beneficial and safe for the patient by the Investigator. In total, the patient can participate in study visits for 60 weeks (██████████). If patients are not on-treatment, the blue-labeled study visits for sampling are canceled. On-treatment patients refers to patients continuing LOAd703 and/or atezolizumab treatment. Patients discontinuing treatment (i.e., off-treatment) can have the final follow-up visit scheduled earlier. The final follow-up visit should be at least ██████████ so that the final endpoint data are collected. After the final follow-up visit at the clinic, patient health status and the overall survival will be recorded until death or End of Study, (see 7.5.3 Survival Follow-Up).

**Figure 1. Study timeline.** Schedule for study treatments, sampling, and follow-up visits. The planned study participation with visits to the clinic for an individual patient spans a maximum of 60 weeks ██████████) provided that either LOAd703 or atezolizumab is continued. Note that shedding samples will be collected ██████████ Further, atezolizumab PK sampling at ██████████ Following the final follow-up clinical visit, patient health status and overall survival will be recorded until death or End of Study (see 7.5.3 Survival Follow-Up).

## 5.3 Study Sites

### 5.3.1 General Description

The patients recruited in this trial will participate in the trial activities at the study sites under the guidance of the site Principal Investigator. As soon as a patient is enrolled in the trial, the Investigator is responsible for the patient.

LOAd703 is administered by i.t. injection. The selection of injectable lesions is decided by the Investigator after consultation with the interventional radiologist. The injections are performed by the radiologist or Investigator following the same procedures as when a biopsy is taken, see "*Instructions for tumor lesion selection for LOAd703 injections and effect evaluation*" in the Investigator Site File.

The hospital personnel involved in this trial have experience and/or training using immunostimulatory adenovirus-based treatments. Study patients are treated in a hospital with a fully equipped emergency care unit. The study nurse/coordinator brings the patient and the LOAd703 virus to the injection suite and stays during the injection, whereupon the patient is transferred to the appropriate hospital unit for monitoring and atezolizumab administration. Trial visits such as sampling and meetings with the study team will also take place at the hospital unit.

